This study is a simple randomized clinical trial, its **objective** is to evaluate the effect of an aerobic physical exercise program on the reduction of triglycerides, blood pressure, abdominal obesity, altered glucose levels, and the increase in HDL in college-level students at the University of Colima, due to the high prevalence of obesity, a sedentary lifestyle, and physical inactivity in Mexican population, all of which contribute to a high risk for the development of metabolic disorders and cardiovascular diseases. **Methods and Materials:** A simple randomized clinical trial will be conducted with a **sample** of 48 voluntary students from the University of Colima, divided into two groups of 24 people. **Instruments:** IPA-Q questionnaire (*Annex 6*), waist circumference (*Annex 7*), blood pressure (*Annex 8*), blood extraction by a venous puncture for HDL, triglycerides, and blood glucose (*Annex 9*), Queen's College Step Test (*Annex 10*). **Procedure:** Once all the information from the tests is collected and processed, inclusion criteria (*table 2*) will be taken into consideration to obtain the total sample. Simple randomization will be carried out through a bag of sealed envelopes that will contain the letter of the group to which the subject belongs. Each participant will draw an envelope, write their name on it and hand it to the supervisor. Afterwards, these envelopes will be opened and participants will be assigned to the groups following the simple blind criteria, according to the letter on the envelope. The Experimental Group will undergo an aerobic physical exercise (APE) program involving jogging, swimming, and static cycling, three times a week with a duration of 60 minutes per exercise session with a progressive intensity, which will start at 57%-63% of the maximum heart rate (HRmax) in the first 4 weeks of the study, and will increase to 64% -76% in the final four weeks, fulfilling the principle of progressive overload. The control group will perform aerobic physical exercise, which will be walking at 57% to 76% of HRmax. **Expected results:** This intervention will lead to favourable changes in the disorders experienced by the intervention population and, at the same time, confirm the effectiveness of the planned aerobic physical exercise in reducing these risks.

Keywords: Exercise, Obesity, HDL, Triglycerides, Hypertension.

1. Introduction

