5.2.2. Specific Objectives

1. To establish the prevalence of metabolic disorders (abdominal obesity, triglycerides, HDL, hypertension, and glucose alterations).
2. To determine and compare the post-intervention level of physical activity using the long version of the International Physical Activity Questionnaire (IPAQ).
3. To determine and compare the post-intervention level of cardiorespiratory fitness through the Queen's College Step Test.
4. Compare post-intervention prevalence levels of metabolic disorders (HDL, triglycerides, abdominal fat, hypertension, blood glucose alterations) in higher education students.
5. Determine the level of association between metabolic disorders and cardiorespiratory fitness pre- and post-intervention.

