5.3 Hypothesis

Hi. The implementation of an aerobic physical exercise program for eight weeks will have effects on at least one of the levels of metabolic disorders such as: the reduction of blood pressure, abdominal obesity, altered glucose levels, and increasing HDL in the study population

H0. The implementation of an aerobic physical exercise program for eight weeks will not have effects on any of the levels of metabolic disorders such as: the reduction of blood pressure, abdominal obesity, altered glucose levels, and increasing HDL in the study population

6. Methods and materials

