6.2 Sample size

The sample size was calculated with a formula to compare two means:

$$n = \frac{K(\sigma_1^2 + \sigma_2^2)}{(\mu_1 - \mu_2)^2}$$

Figure 5. Applied formula to calculate the sample size.

Source: Taken from García in 2013(104).

The sample size was determined through a study that assessed the impact of physical training on metabolic alterations. The pre-intervention measurements were 131.31 ± 22.53 , and the post-intervention measurements were 116.90 ± 12.88 (65)

Error $\alpha = .05$

Error $\beta = 0.2$ (20%)

Power $1 - \beta = .8$ (80)

$K = 6.2$

$\sigma^2 = 22.53$

$\sigma^2 = 12.88$

$\mu_1 = 131.31$

$\mu_2 = 116.90$

$n = 20 \pm 20\%$.

$n = 24$ subjects per group

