condition to conclude their assessments, if not, they will be monitored until their answer is affirmative). Subsequently, after completing sample collection and assessments, the control group (A) will continue with the same dynamics as in the initial weeks. The experimental group (B) will maintain the same exercises (jogging, aquatic activities, and stationary cycling), but their intensity may be adjusted from 64% to 76% of the maximum heart rate if favourable results are obtained from the cardiorespiratory fitness test (*annexe 11*), since this shows the level of evolution of the subject after the initial intervention and thus, the FITT-VP principle in exercise prescription would be fulfilled.

At the end of the last 4 weeks of the aerobic physical exercise program, the same sampling will be concluded; Abdominal circumference (*annexe 7*), arterial pressure (*annexe 8*), blood collection by venipuncture for HDL, triglycerides and glycemia (*annexe 9*), and the Queen's College step test will be performed (3 minutes) (*annexe 10*) (after completing all the tests, every participant will receive refreshments and will be asked if they are in good condition to conclude their assessments, if not, they will be monitored until their answer is affirmative), finishing the proposed intervention protocol.

10. Study flowchart

11. Statistical analysis

The statistical analysis will be conducted using the Statistical Package for the Social Sciences (SPSS) Statistics 26 from Business Machine (IBM). Descriptive statistics will be carried out, including measures of central tendency for the variables of age, sex and IPA-Q. Normality tests will be applied such as Kolmogorov-Smirnov for samples > 50 , and Shapiro-Wilk for samples < 50 . For the levels of triglycerides, glucose, HDL (High-Density Lipoprotein), abdominal circumference, and cardiorespiratory fitness, paired-sample T-tests will be used if the data follow a normal distribution, but if they do not, the Wilcoxon signed-rank test will be employed. To compare the control and experimental groups, independent-sample t-tests will be used if the data is normally distributed, otherwise the Mann-Whitney U test will be used. Likewise, a multivariate analysis will be carried out to relate the influence of physical exercise

on metabolic alterations. A significance level of $p \leq 0.05$ will be considered statistically significant.

12. Ethical considerations

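### Section 11 does not say which test decides the hypothesis, or whether arms are compared on values or changes; rest conclusions on the week-8 between-arm difference from a baseline-adjusted ANCOVA

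*Combined protocol and SAP*

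**What the plan says.** Section 11 lists three kinds of analysis and gives them one threshold, p ≤ 0.05.

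- **Within-arm tests.** The outcomes covered are introduced by "For the levels of triglycerides, glucose, HDL (High-Density Lipoprotein), abdominal circumference, and cardiorespiratory fitness". In these cases the plan is that "paired-sample T-tests will be used if the data follow a normal distribution", with Wilcoxon signed-rank as the fallback. The pair of visits is not named, and blood pressure is not in the list.
- **Between-arm tests.** "To compare the control and experimental groups, independent-sample t-tests will be used if the data is normally distributed", with Mann-Whitney as the fallback. No visit, quantity (value or change) or baseline adjustment is given.
- **A third analysis.** "a multivariate analysis will be carried out to relate the influence of physical exercise", the target being metabolic alterations. This names an exposure and an outcome domain, but no model or covariates.

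The hypothesis in section 5.3 is that the eight-week programme "will have effects on at least one of the levels of metabolic disorders such as: the reduction of blood pressure"; the other disorders listed are abdominal obesity, glucose and HDL. It names no comparator. The abstract's expected results read: "This intervention will lead to favourable changes in the disorders experienced by the intervention population and, at the same time, confirm the effectiveness" (that is, of the exercise programme).

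Section 9 has outcomes measured at baseline, week 4 and week 8. It gives the control arm supervised walking three times a week at 57% to 76% of maximum heart rate. Section 9 and Annexe 11 disagree on the length of those walks and must be reconciled, but on either version the control arm is active.

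**The concern.** Three analyses share one threshold and none is ranked, so any of them could be reported as the answer. This matters most for the paired tests. Both arms train, and participants enter because at least one metabolic value is abnormal. A fall from baseline in the experimental arm can therefore occur without any advantage over walking. The abstract describes success as change in the intervention population. Section 6.2 also sizes the trial on a pre-to-post change in a cited study. Both make the within-arm reading easy to slip into.

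The second gap is the quantity compared between arms. Week-8 values and changes from baseline are both valid under randomisation, but they differ in precision. If the choice stays open until the data are seen, the 5% error rate is lost.

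**Working it through.** **Inputs.** From section 6.2: means 131.31 and 116.90 mg/dL (difference 14.41), SDs 22.53 and 12.88, K = 6.2, 24 per group. Section 2.4 shows that these are triglycerides before and after a programme in a cited study. Section 6.2 gives SDs for no other outcome, and the section 5.3 hypothesis does not name triglycerides, so the figures are illustrative. My assumptions are: the same SDs in both arms, pre-post correlation r = 0.3 / 0.5 / 0.7, and two-sided 0.05 (section 11 states no sidedness).

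**The plan's own figure.** n = K(SD₁² + SD₂²)/(μ₁ − μ₂)² = 6.2 × (507.60 + 165.89)/207.65 = 20.11, stated as 20; 20 × 1.2 = 24. This reproduces. The 14.41 in it is a pre-to-post change, not a difference between arms.

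**Paired test when the arms do not differ.** The variance of the change is 22.53² + 12.88² − 2r(22.53)(12.88) = 499.4 / 383.3 / 267.2, so the SD is 22.35 / 19.58 / 16.35. The noncentral t has df 23 and noncentrality (shift/SD) × √24.

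| Equal fall in both arms | r = 0.3 | r = 0.5 | r = 0.7 |
|---|---|---|---|
| 14.41 mg/dL | 0.86 | 0.93 | 0.99 |
| 7.2 mg/dL (half) | 0.33 | 0.41 | 0.54 |

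Each entry is the probability that the experimental arm's paired test is significant. The true between-arm difference is zero throughout.

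**Choosing the quantity after seeing the data.** In simulated trials with no effect, the week-8 t-test, the change t-test and ANCOVA each hold about 5%. The chance that at least one of the first two is significant is about 9–10% across these correlations.

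**Between-arm difference detectable with 80% power.** This uses the noncentral t, standard error SD × √(2/24), and df 46 (45 for ANCOVA). The SD is that of the week-8 value, that of the change, or the week-8 SD × √(1 − r²) for ANCOVA. The second set of rows uses one common SD, √((22.53² + 12.88²)/2) = 18.35.

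| SDs assumed | Analysis | r = 0.3 | r = 0.5 | r = 0.7 |
|---|---|---|---|---|
| 22.53 / 12.88 | week-8 values | 10.6 | 10.6 | 10.6 |
| | changes | 18.5 | 16.2 | 13.5 |
| | ANCOVA | 10.2 | 9.2 | 7.6 |
| 18.35 common | week-8 values | 15.2 | 15.2 | 15.2 |
| | changes | 17.9 | 15.2 | 11.7 |
| | ANCOVA | 14.5 | 13.1 | 10.8 |

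ANCOVA is best in every column. Its smallest gains over the better alternative are about 5% (10.2 against 10.6, or 14.5 against 15.2, at r = 0.3) and 8% (10.8 against 11.7 at r = 0.7 with the common SD).

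**The at-least-one rule.** Fixing the test does not settle this. With the four domains of section 5.3 each tested at 0.05 and independent, the family-wise error is 1 − 0.95⁴ = 18.5%. With systolic and diastolic pressure counted separately it is 1 − 0.95⁵ = 22.6%. Correlated outcomes give less.

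**The case against.** The strongest reply is that the plan already contains the right comparison. The trial is randomised, the sample size uses a two-group formula, and section 11 includes a between-arm test. The abstract's expected results are not a decision rule. That stands: a reader might infer that efficacy will be judged within the arm, but the documents do not say so. They only fail to rule it out.

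Three other stronger readings also fail.

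- **That the time point is wholly open.** If the visit were free as well as the quantity, the simulated error for one outcome is 16.5%. But the hypothesis speaks of an eight-week programme, the specific objectives refer to levels after the intervention, and section 9 uses the week-4 fitness test to decide on intensity. Week 8 is the natural reading; it only needs writing down.
- **That a paired test would usually be significant with no programme effect.** This holds if the walking arm also falls by 14.41, a change seen in a 13-week programme with four sessions a week. At half that fall it does not hold for r = 0.3 or 0.5.
- **That analysing changes is always much less precise.** That follows from applying the two unequal SDs of one cited study to both arms. With a common SD, changes equal week-8 values at r = 0.5 and beat them at 0.7.

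An unadjusted week-8 t-test is also valid. The fault is that the quantity is left unstated. ANCOVA is recommended because it is at least as precise as either alternative in every case examined and uses baseline data already collected.

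**Conclusion.** The point holds as a gap in specification with an inexpensive remedy, not as an invalid analysis. Section 11 does not fix which test decides the hypothesis or which quantity is compared between arms. A within-arm p-value cannot answer the question because both arms exercise. With no between-arm effect, such a p-value would be significant in 33% to 99% of trials over the shifts and correlations shown. Leaving values or changes open costs about 4 to 5 percentage points of type I error per outcome.

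The unranked tests, the unstated quantity and the active control are read directly from the documents, and confidence in them is high. The mg/dL figures are less certain. They cover triglycerides only and rest on assumed correlations and on SDs carried over from one cited study to both arms. The ordering that puts ANCOVA first holds under both SD choices; the size of its advantage does not.

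**What to change.** Change section 11 as follows.

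1. State that conclusions rest on the between-arm difference at week 8, estimated by ANCOVA with the baseline value of that outcome as covariate, and reported as an adjusted mean difference with 95% CI.
2. Add systolic and diastolic blood pressure, which the hypothesis covers but section 11's outcome list omits.
3. Report week-4 results and within-arm changes descriptively only.
4. Because the hypothesis is met by an effect on any one disorder, name one primary outcome, or apply Holm to every outcome on which a conclusion will rest. Label any outcome left outside that family as secondary or exploratory (triglycerides or estimated VO₂max, for example).

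The cost is a few sentences and one linear model per outcome in SPSS 26, which the plan already uses. No new data are needed. The undefined multivariate analysis and the association objective in section 5.2.2 ("Determine the level of association between metabolic disorders and cardiorespiratory fitness pre- and post-intervention") need their own definitions, but those are separate matters.

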13.2 Material Resources

Table 8. Materials and costs

Resource Type	Unit	Amount	Cost per unit	Total cost	Elements are available.
Computer	Piece	1	\$ 7,000	\$ 7,000	✓
Printer	Pieza	1	\$ 3,794	\$ 3,794	✓
Paper	Pack of sheets	4	\$ 500	\$ 2,000	

Pens	Pack of 20	2	\$ 130	\$ 260	✓
Speaker	Piece	1	\$ 2,000	\$ 2,000	✓
USB	Piece	1	\$ 100	\$ 100	✓
40 cm Bench	Piece	1	\$ 750	\$ 750	
Lipid Profile Test	Unit	150	\$ 17,250	\$ 17,250	
Fasting Plasma Glucose Test	Unit	150	\$ 8,304	\$ 8,304	
BD Vancutainer SST Yellow Cap Tube	Box	100	\$350	\$350	
Green Flash Pulse Needle / BD Ancuntainer 216x1-1/1m 0.8x30 mm	Box	1	\$ 600	\$ 600	
Centrifuge; Centrifuge 580412-15 amp EPPENDOR Version	Unit	1	\$15,142.17	\$15,142.17	✓
Pipette Tips for 1000 Microliter Transferpette	Unit	1	\$ 1,000	\$ 1,000	

Axygen 1.5ml Microtube, Eppendorf Type, 500 pcs	Box	1	\$ 900	\$ 900	
Autoclave/ Sterilizer	Unit	1	\$ 45,321	\$ 45,321	✓
Wrist Digital Blood Pressure Monitor	Piece	1	\$ 800	\$ 800	
Metallic Measuring Tape	Piece	1	\$ 100	\$ 100	
Uline Silent Tape - 3.1 Mil Thickness, 3" x 55 yards, Transparent, 75 mm x 50 M	Unit	1	\$ 300	\$ 300	
Folio labels	Box	1	\$ 150	\$ 150	
Powder-Free Nitrile Examination Gloves, Blue	Box	1	\$ 140	\$ 140	
Multitube Sample Rack	Unit	10	\$ 30	\$ 300	
-40° Freezer	Unit	1	\$ 123,455	\$ 123,445	✓

Soft Tor Medimetrics Venous Tourniquet for Blood Extraction	Unit	1	\$ 100	\$ 100
Cotton Swabs 500g with 1000 Protec Pellets	Box	1	\$ 170	\$ 170
8.5 L Plastic Container for Infectious Biological Sharps	Unit	1	\$ 150	\$ 150
Red Bag for Biological Waste 50x60 cm, Pack of 20	Unit	4	\$ 100	\$ 400
3m Steam Sterilization Indicator Tape, 18mm x 55m	Unit	2	\$ 130	\$ 260
Kraft Wrapping Paper Roll, 80 cm, 17.5 kg (227.50 m), 125gsm	Unit	1	\$ 800	\$ 800
Cones	Piece	1	\$ 175	\$ 175
Ropes	Piece	5	\$50	\$250

Hoops	Piece	10	\$38	\$380
Training Steps	Piece	3	\$ 235	\$ 705
Stopwatch	Piece	1	\$ 500	\$ 500
Polar H10 Heart Rate Monito	Piece	4	\$2.499	\$9,996
Total Investment:				\$ 237,602 \$ 44,602

Source: Self-made based on reference (108)

14. Schedule of activities

Numero	Activities	SCHEDULE OF ACTIVITIES																							
		Months - programed calendar																							
		1	2	3	4	5	6	7	8	9	10	11	12	13	14	15	16	17	18	19	20	21	22	23	24
1	Continuous modifications for document improvement.	■	■	■	■	■	■	■	■	■	■														
2	Protocol presentation to the Medicine Bioethics Committee									■	■														

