2.2.3. Test and diagnosis of systemic arterial hypertension

For the diagnosis of systemic arterial hypertension (SAH), the test must be performed with a stethoscope and a sphygmomanometer (Baumanometer) with a properly calibrated band. The process begins with the patient sitting for 5 to 10 minutes to stabilize blood pressure. Afterwards, the Baumanometer band will be wrapped around the arm, it should be 2 or 3 cm above the fold of the elbow joint. Next, the brachial artery must be palpated to be able to place the bell of the stethoscope at the level of the brachial artery (The centre of the camera must align with the brachial artery). Once these steps have been completed, the handle of the manometer will be inflated until a pressure of 160 mmHg is reached. After reaching this reference, the valve will be opened gradually with a speed of 2 to 3 mmHg/second, listening in turn to the pulsations emitted by the body to determine systolic and diastolic blood pressure

(35). If the patient obtains a systolic blood pressure of >130 mmHg and diastolic blood pressure of >80 mmHg, an alteration in blood pressure must be confirmed (36). Annex 5.

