Arterial Hypertension	Subject's systolic and diastolic blood pressure measured in mercury millimeters (mmHg)	Quantitative Continuous Ratio	It is considered an alteration when: Males > 130/85 mmHg Females > 130/85 mmHg	Sphygmomanometer
Physical Activity Level	Physical Activity performed by the subject 7 days before the survey	Qualitative Ordinal	PA: Low, Medium, High	IPA-Q (International Physical Activity Questionnaire)
Physical Fitness Test: Aerobic	Subject's cardiorespiratory capacity using an	Qualitative Ordinal	Very Poor Poor Average	Quee's College Step Test

Capacity	effort test.		Good Excellent Superior	
----------	--------------	--	-------------------------------	--

Source: self-made based on the reference (11,105).

Table 6. Independent variables

Variable	Operational definition	Nature	Scale	Instrument
Aerobic physical exercise	Individually adapted aerobic physical exercise program meeting the WHO 2021 criteria and the FITT Principles.	Quantitative Continuous Ration	57% - 76%	Prescription

Source: self-made.

Table 7. Intervinient variables

Variable	Operational definition	Nature	Scale	Instrument
Age	Chronological age in years	Quantitative Continuous	18 - 24 years	Survey
Sex	Genetically corresponding sex	Qualitative Dichotomous nominal	Male and Female	Survey

Source: self-made.

8. Location for carrying out the protocol

University of Colima's Sports Center (central campus).

9. Study Procedure

Once the project is approved by the Bioethics Committee from the Faculty of Medicine at the University of Colima (Annex 1) and the Ethics Committee from Colima's Regional Hospital (Annex 2), annexing a no-conflict of interest letter (Annex 3), letters of intent will be prepared and sent to the directors of the faculties within the central campus of the University of Colima (Annex 4). Their purpose is to inform them about the project's generalities, obtain permission to share it with the students and address any questions they may have

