_____ **hours per day**
_____ **minutes per day**

27. During the **last 7 days**, how much time did you usually spend **sitting** on a **weekend day**?

_____ **hours per day**
_____ **minutes per day**

This is the end of the questionnaire, thank you for participating.

Annexe 7. Test and cut-off points for abdominal obesity

For this test, a certified measuring tape will be used and it will also have the objective of determining the abdominal circumference taking into account the morphophysiological parameters established by the International Society for the Advancement of Kinanthropometry (ISAK) and a marker (109). The subject must be placed in an anatomical position and then will be told to raise his arms crossed at chest height, then the upper edge of the iliac crest will be identified by marking it with the marker, and after that the lower edge of the last rib will be identified, so a marking will be made, then the two established references will be taken to identify the middle area of the markings, then the abdomen will be surrounded with the tape and the subject will be told to breathe normally and at the end of this the circumference will be taken (Table 1).

Annexe 8. Blood pressure cut-off points.

Tabla 9. Estadios de la presión arterial.

X	Systolic (mmHg)	Diastolic (mmHg)
Normal blood pressure	<120	< 80
High	Between 120 – 129	< 80
Hypertension stage 1	Between 130 – 139	Between 80 - 89
Hypertension stage 2	>140	> 90

Source: Reference table for classification of hypertension based on reference (35,110)

Annexe 9. Test and cut-off points for hyperglycemia.

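### The materials list's only blood pressure device is a wrist monitor, which cannot carry out the one measurement method the document describes, and Annexe 8 gives cut-offs but no procedure

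*Combined protocol and SAP*

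**What the plan says.** Four places bear on how blood pressure is measured.

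- **Section 13.2, Table 8.** One piece of "Wrist Digital Blood Pressure Monitor" at $800, not ticked as already available. No stethoscope, arm cuff or other blood pressure device is listed.
- **Section 2.2.3 (theoretical framework).** For diagnosis, "the test must be performed with a stethoscope and a sphygmomanometer (Baumanometer) with a properly calibrated band". After 5 to 10 minutes seated, "the Baumanometer band will be wrapped around the arm, it should be 2 or 3 cm above the fold of the elbow joint". The reading is taken during deflation, "listening in turn to the pulsations emitted by the body to determine systolic and diastolic blood pressure". The section ends with a pointer to Annex 5, which section 9 identifies as the consent form.
- **Section 7, Table 5.** The instrument is given as "Sphygmomanometer", with no type or measurement site.
- **Section 9 and Annexe 8.** All three assessment rounds refer to Annexe 8 for blood pressure. That annexe is headed "Annexe 8. Blood pressure cut-off points" and consists of a staging table.

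Section 6.3 (Table 4) admits a student who has at least one metabolic alteration, and hypertension is one of the five. Section 9 makes the screening tests the baseline. Specific objectives 1 and 4 in section 5.2.2 concern the prevalence of disorders, hypertension included.

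**The concern.** The device to be bought and the method described do not match. Staff who follow section 9 to Annexe 8 find nothing on device, site, rest, posture or number of readings. The budget gives them a wrist monitor, and the only method in the text is one that this monitor cannot carry out.

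Blood pressure is read against fixed thresholds, both to decide entry and to count who has hypertension before and after the programme. If the device reads systematically high or low relative to the method described, some students near the threshold are classified differently with no difference in their true pressure. That changes who is enrolled and what prevalence is reported.

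**Working it through.** The plan gives no figure to reproduce, so the main check sets the passages side by side.

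1. **Can the listed device perform the described method?** No. Section 2.2.3 needs a cuff above the elbow and listening over the brachial artery. A wrist digital monitor does neither.
2. **Does Table 5 settle it?** No. The term is generic. It can cover a digital monitor or mean the arm device of section 2.2.3.
3. **Does Annexe 8 settle it?** No. It has stages only. Annexes 7, 9 and 10, by contrast, describe how abdominal circumference, blood sampling and the step test are done.
4. **Does another cross-reference lead to a procedure?** Not in the available text. Section 2.2.3 points to the annex that section 9 calls the consent form.
5. **Where would an offset matter?** At the entry threshold (Table 4 with Table 5) and in prevalence (objectives 1 and 4).

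**Illustration only.** No input below except the 130 mmHg threshold (Table 5) comes from the documents. Assume that true systolic pressure is Normal with mean 120 and SD 11 mmHg, and that the device adds a constant b. Then P(read > 130) = 1 - Φ((130 - 120 - b)/11).

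| b (mmHg) | (10 - b)/11 | Share read > 130 |
|---|---|---|
| -5 | 1.364 | 0.086 |
| 0 | 0.909 | 0.182 |
| +5 | 0.455 | 0.325 |

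The same three values show why means and prevalence behave differently. Suppose two groups truly differ by 5 mmHg, with means of 120 and 115. With no offset, their shares above 130 differ by 0.182 - 0.086 = 0.096. With +5 mmHg added to both groups, the shares differ by 0.325 - 0.182 = 0.143. The difference in means is 5 mmHg in both cases.

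**The case against.** The strongest reply is that section 2.2.3 is background. It sits in the theoretical framework, and section 9 never cites it. The same chapter describes bioimpedance, which the trial does not use. Table 5's generic term is compatible with the wrist monitor. On that reading no two trial instruments conflict. This stands as far as it goes: the trial never explicitly adopts the arm-cuff method. But if section 2.2.3 is not the method, the available text has none.

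A second reply is that Table 8 is a budget and may be incomplete. It omits the metronome of Annexe 10 and the stationary bicycles of Table 12. The justification (section 3) says the team has the infrastructure for screening, so a stethoscope and cuff may be on hand. That is possible. Yet Table 8 does list and tick owned equipment, and a wrist monitor has no place in the only method described.

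A third reply is that a constant offset, or one that shifts equally in both groups, largely cancels in the planned between-group comparison of means. That is correct. In addition, section 11 does not name blood pressure among the variables for the paired tests. The reply does not extend to thresholds.

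A reader might go further and infer several things that the documents do not support:

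- **A change of device between rounds, read as an exercise effect.** Table 8 shows a single piece, and nothing indicates switching.
- **A baseline resting on a single reading.** The number of readings is not stated.
- **A ceiling from the inflation level in section 2.2.3** ("inflated until a pressure of 160 mmHg is reached") **on top of wrist error.** The ceiling arises only if the manual method is used and the wrist error only if it is not, and the trial never adopts that text as its procedure.

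**Conclusion.** The point holds as a gap in measurement specification. The one device budgeted cannot perform the one method described, and the annexe to which staff are sent has no method. The consequence is limited to threshold-based uses, namely entry through hypertension and prevalence before and after the programme. It does not show that the between-group comparison of mean blood pressure is biased.

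The size is unknown, because the documents give no device offset. The 9% to 32% range follows from an assumed mean, SD and offset. It shows how sensitive a cut-off can be and does not estimate this monitor's error. The finding also rests on the available text: some pages were removed, and the Annexe 15 layout of the tests cannot be read here. It is a cheap improvement worth making before screening, because the screening values become the baseline and pre-training readings cannot be repeated once the programme has begun.

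**What to change.** Reconcile section 2.2.3, Table 5, Table 8 and Annexe 8.

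- Name one validated upper-arm device in Table 5, Table 8 and Annexe 8, in place of the wrist monitor.
- Write one procedure into Annexe 8: seated rest as in section 2.2.3 (5 to 10 minutes), same arm at heart level, two readings averaged, and the same device at all three rounds.
- Correct the pointer in section 2.2.3 so that it leads to Annexe 8.

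Averaging has a precedent in the document, since section 2.2.1 recommends at least two measurements for abdominal circumference. The cost is a replacement for the wrist monitor (budgeted at $800), a few minutes per participant, and the annexe wording. No extra staff are needed.
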